2.11 Additional Evaluations

Exploratory analysis comparing results from study NN7008-3543, NN7008-3545, NN7008-3568 and NN7088-3776 with results from this study will be performed and reported separately. This analysis will include overall comparisons as well as individual comparisons for patients participating in one of the above listed trials and this NN7088-3859 trial, if the patient through the informed consent has given approval of such comparison of data.

3 Changes to the statistical analyses planned in the protocol

It has been clarified that treatment requiring bleeding episodes occurring in multiple locations with the same start time will be calculated as one bleed. This is in accordance to the initial setup of how data could be captured in the diary and electronic case report form (eCRF), but some changes have been made in the eCRF by mistake at a later time point where auto-query has been added to enquire all bleeding episodes which were associated with multiple locations to be captured as separate episodes.

As a conservative approach, the worst response will be used in case multiple haemostatic responses were registered for multiple bleeding locations with the same start time.

None of the non-joint bleeds will be considered as re-bleeds even if they occurred within 72 hours as the specific location is not captured in the database.

A conservative approach will be used to calculate the planned exposure time for withdrawals such that the maximum expected exposure time will be used.

An additional sensitivity analysis is added for the analysis of the ABR to investigate the robustness of the assumption that the treatment requiring bleeds can be modelled adequately using a Poisson distribution with overdispersion. The additional sensitivity analyses uses modelling based on the negative binomial distribution

It was added that ABR will be analysed when there are at least 5 patients in total and when at least one bleed was observed, in order to provide reliable estimates.

At the end of trial:

Efficacy data:

As a sensitivity analysis, analysis without imputation to planned duration will be performed. The other sensitivity analyses performed in the pivotal reporting are no longer applicable, since this was already addressed in the previous interim reportings.

Calculation of ABR by month for a given treatment regimen has been defined to be based on the first consecutive period on the treatment regimen to ensure that a effect over time is not influenced by time on other treatment regimens.

Calculation of ABR by calendar month has been defined to be done by shifting calendar month half a year for countries in the southern hemisphere (i.e. Brazil and Australia). This is done to take the difference in seasons between the southern and northern hemisphere into account.

The ABRs defined to be calculated based on a sub-selection consisting of data from extension phase part 2, will not be done, since patients have differing trial durations when entering extension phase part 2 and therefore ABRs for such a sub-selection is of limited value.

PK data:

Since patients are allowed to change treatment regimen at any time during the extension phase part 2 and since the visits intervals are different for the prophylaxis treatment regimens, FVIII activity data will be summarised by visit only for incremental recovery. Since incremental recovery is dose-normalised activity increase this will not be affected by a possible regimen and dose change.

Plots of pre-dose activity measurements will not be created since the plots have been evaluated to contribute with no relevant information.

PRO data:

PRO endpoints for extension phase part 2 will be summarised by grouping of time since first dose, since timing of visits depend on treatment regimen and since patients are moving between treatment regimens.

Safety data:

Adverse Events and Serious Adverse Events will be summarised by treatment regimen and all other safety endpoints will be presented by listings and individual graphical representation only. Safety data consists of accumulated data from the trial.

4 References

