4.2.4 Timeframe for evaluation of the endpoints

The pharmacokinetic endpoints will be based on assessments performed from 1 hour prior to and up to 96 hours after administration for visit 2a and Visit 7.

All efficacy endpoints will be analysed and reported separately for the Main Phase, for the Extension Phase part 1 and for the Extension Phase part 2 of the trial. All safety endpoints will be reported separately for the Main Phase, for the Extension Phase part 1 and for the Extension Phase part 2 as well as based on accumulated data (Main Phase + Extension Phase part 1 and Main Phase + both Extension Phases).

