Adverse events, consumption of N8-GP, recovery and trough levels will be summarised based on accumulated data (Main + Extension Phase part 1) by treatment regimen combining the every 4 day dosing regimens. In addition, separate summaries including data from part 1 only will be presented by treatment regimen for the randomised subset of patients to support the main objective of part 1 of the Extension Phase.

Other safety endpoints will be summarised based on accumulated data (Main Phase + Extension Phase part 1). Binding non-inhibitory antibodies will be listed.

PRO endpoints at end the Extension Phase part 1 will be evaluated and presented as described in section 18.9.

Data from part 2 of the Extension Phase

All evaluations/summaries based on accumulated data in part 1 will be repeated in part 2, accumulating data from the entire trial (Main Phase + Extension Phase part 1 + part 2).

In addition, ABR during part 2 will be summarised for the prophylaxis regimens combined. Furthermore, ABR during each 6 month interval in this period will be summarised by prophylaxis regimen used during that period.

Frequency and time used of treatment regimens will be summarised for the different treatment prophylaxis regimens used during the Extension Phase part 2.

PRO endpoints at end of each year in Extension Phase part 2 and at end of Extension Phase will be evaluated and presented as described in section 18.9.

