Only treatment requiring bleeding episodes will be considered in the above evaluations of ABR. Incidence rate of FVIII-inhibitor and haemostatic effect of N8-GP when used for treatment of bleeding episodes will be evaluated based on accumulated data (Main Phase + Extension Phase part 1).

Adverse events, consumption of N8-GP, recovery and pre-dose levels will be summarised based on accumulated data (Main + Extension Phase part 1) by treatment regimen combining the every 4 day dosing regimens. In addition, separate summaries including data from part 1 only will be presented by treatment regimen for the randomised subset of patients to support the main objective of part 1 of the Extension Phase.

Other safety endpoints will be summarised based on accumulated data (Main Phase + Extension Phase part 1). Binding non-inhibitory antibodies will be listed.

PRO endpoints at end the Extension Phase part 1 will be evaluated and presented as described in section 18.9.

Data from part 2 of the Extension Phase

The main objective of extension phase part 2 is to collect long term safety and efficacy data.

ABR will be calculated as for the co-primary endpoint in the main phase, but based on the accumulated data, i.e. combined data from main phase, extension phase part 1 and extension phase part 2. Furthermore, sensitivity analyses are performed based on actual bleeding episodes and exposure times (i.e. without imputation for withdrawn patients).

Incidence rate of FVIII-inhibitor and haemostatic effect of N8-GP when used for treatment of bleeding episodes will be evaluated based on accumulated data.

Adverse events and consumption of N8-GP will be summarised based on accumulated data by treatment regimen.

Incremental recovery will be summarised by visit for extension phase part 2 and furthermore be presented graphically in the following ways:

- By N8-GP production process (extension phase part 2 data)
- According to Anti-PEG-antibody status (accumulated data)

For Anti-CHO HCP-antibodies, the number of negative/positive samples will be summarised by visit.

Other safety endpoints will be listed and/or plotted based on accumulated data.

-

PRO endpoints for extension phase part 2 will be summarised by time since first dose (since timing of visits depend on treatment regimen). Time grouping will span a year, i.e. grouping being “1 - <2 years”, “2 - <3 years”,.... The two prophylaxis regimens will be considered as a combined prophylaxis treatment regimen.

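### SAP section 3 drops the protocol's part 2 bleeding-rate summaries for a reason that does not justify it, and the outputs that remain only partly replace them

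*SAP*

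**What the plan says.** Protocol 4.2.4, repeated at the start of section 18, sets the general rule that efficacy "endpoints will be analysed and reported separately for the Main Phase, for the Extension Phase part 1 and for the Extension Phase part 2". Protocol 18.10 then names two part 2 outputs. The first: "In addition, ABR during part 2 will be summarised for the prophylaxis regimens combined". The second: "Furthermore, ABR during each 6 month interval in this period will be summarised by prophylaxis regimen used during that period". The same section also orders the accumulated evaluations from part 1 to be repeated over the whole trial. Amendment 18 later reduced part 2 safety parameters other than adverse events to listings and plots, and left the ABR summaries alone.

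SAP section 3, under the end-of-trial changes, states: "The ABRs defined to be calculated based on a sub-selection consisting of data from extension phase part 2, will not be done". The reason follows in the same sentence: "patients have differing trial durations when entering extension phase part 2 and therefore ABRs for such a sub-selection is of limited value". SAP 2.10 computes the part 2 ABR "based on the accumulated data, i.e. combined data from main phase, extension phase part 1 and extension phase part 2", with a version without imputation. SAP 2.2.2 keeps ABR estimates with 95% confidence intervals by regimen, and a monthly bleeding rate by regimen limited to the first consecutive period on that regimen.

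**The concern.** SAP 2.10 gives long-term safety and efficacy data as the main objective of part 2. Whether protection is maintained is a question about bleeding in the later person-time, and the cancelled summaries were the outputs that isolated it. An ABR accumulated from first dose averages early and late experience, so a later change shows only in part.

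The reason given is weak on the plan's own terms. An ABR is a rate per unit time. Protocol 18.1 uses log observation time as an offset expressly to deal with differing treatment lengths, and the Main Phase analysis pools exposures of roughly 7 to 19 months on that basis. The SAP still summarises incremental recovery for part 2 alone.

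**Working it through.** **1. The plan's own figures.** No target or power is stated for a part 2 ABR. The two reference rates used below reproduce. The weighted historical prophylaxis mean is (85×10 + 107×6.3 + 49×4.9 + 94×3.9 + 27×8.3 + 32×10.3)/394 = 6.81, and 6.8 × 1.25 = 8.5.

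**2. Do differing durations invalidate the rate?** The quasi-Poisson rate (log-time offset, Pearson scale) was simulated with 120 patients, a true rate of 6.8, over-dispersion 5 at one year and 4,000 runs. With equal 3-year durations the mean estimate was 6.80 and 95% interval coverage was 94%. With durations from 0.5 to 4.1 years the mean was 6.81 and coverage 93%. Unequal lengths do not bias the rate. Time on trial before part 2 does not enter a part 2 rate at all.

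**3. How much does accumulation dilute?** Inputs:
- Main Phase exposure T0: 1.0 year (expected mean, protocol 18.1) to 2.25 years (27-month maximum, protocol 5.1).
- Part 1 exposure T1: 24/52 = 0.46 year (SAP 2.2.2).
- Part 2 exposure T2: start taken as the last quarter of 2014 (protocol section 7, end of part 1). This gives about 2.7 years to the SAP cut-off of 15 August 2017, or about 4.1 years to the planned last visit of 3 December 2018.
- These lengths are assumptions from planned dates. The last two rows below assume that only 60% of part 2 time is realised.

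Part 2 share: w = T2/(T0 + T1 + T2). Accumulated rate: (1 − w) × earlier rate + w × part 2 rate. A 50% rise in part 2 therefore shows as w × 50%. With an earlier rate of 6.8, a part 2 rate of 8.5 shows as 6.8 + 1.7w, and the accumulated rate reaches 8.5 only when the part 2 rate reaches 6.8 + 1.7/w.

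| T0 | T2 | w | 50% rise shows as | Part 2 rate 8.5 shows as | Part 2 rate needed for accumulated 8.5 |
|---|---|---|---|---|---|
| 1.0 | 4.1 | 0.737 | 36.9% | 8.05 | 9.11 |
| 1.0 | 2.7 | 0.649 | 32.4% | 7.90 | 9.42 |
| 2.25 | 4.1 | 0.602 | 30.1% | 7.82 | 9.62 |
| 2.25 | 2.7 | 0.499 | 24.9% | 7.65 | 10.21 |
| 1.0 | 0.6 × 4.1 | 0.627 | 31.4% | 7.87 | 9.51 |
| 2.25 | 0.6 × 2.7 | 0.374 | 18.7% | 7.44 | 11.35 |

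**4. Every-7-day dosing.** This regimen starts in the extension, so T0 = 0. For a patient on it from part 1 onward, w = 2.7/(0.46 + 2.7) = 0.854 to 4.1/(0.46 + 4.1) = 0.899, and a 50% rise shows as 42.7% to 44.9%.

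**5. What does the monthly summary cover?** For a patient who never switches it runs into part 2. For a patient first moved to every-7-day dosing in part 2, that curve is part 2 data. For a patient who switches and later returns to an earlier regimen, the time after the return is excluded. The calendar-month summary addresses season, not time on treatment, so that later time appears in no output resolved by time on trial.

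**The case against.** The strongest case for the SAP runs as follows.

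- **The loss is limited.** A reader might infer that long-term efficacy is now judged only on data diluted by the earlier phases. The documents do not support that. The monthly ABR is kept to examine effect over time and extends into part 2, and the every-7-day ABR contains no Main Phase data. This stands.
- **The accumulated ABR is not a SAP invention.** Protocol 18.10 orders it. The cancelled items were extra descriptive summaries and no hypothesis test is lost. This stands.
- **The offset comparison is incomplete.** Main Phase exposures differ in length from a common start at first dose. Part 2 entry occurs at different times since first dose, and an offset does not align those starting points. The plan also added a 12-month sensitivity analysis for varying Main Phase durations. This stands as a caution about trends, but it calls for realignment rather than cancellation. The SAP makes that choice itself for patient-reported outcomes.
- **The 6-month table no longer fits.** It was written when a regimen change required at least 6 months on the same regimen. Amendment 14 struck that condition (protocol 5.3.1), so one interval can span two regimens. Switching also depends on bleeding, so by-regimen rates are selected on outcome. This stands and shapes the fix. The same selection affects the later months of the retained monthly curves.
- **The first-period restriction has a purpose.** It keeps time on other regimens out of the curve, and the omitted time remains in the accumulated ABR. True, but the accumulated ABR is not resolved by time.

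**Conclusion.** The concern holds in limited form. SAP section 3 removes two planned part 2 summaries and departs from the protocol's rule on separate reporting. Its reason does not show that a part 2 rate is invalid.

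The consequence is partial masking. With part 2 at about 37% to 74% of person-time, a 50% rise shows as about 19% to 37% in the accumulated ABR. A part 2 rate of 8.5 after an earlier rate of 6.8 shows as about 7.65 to 8.05 if the full planned part 2 time is realised. These ranges rest on planned dates and on the 60% scenario, not on observed exposure. They apply to regimens that began in the Main Phase. For every-7-day dosing from part 1 onward the masking is small.

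A reader might also infer selective reporting, because the SAP is dated 14 January 2019 in an open-label trial. The documents do not support that inference. The change is listed openly with a reason, and they do not show when it was decided or what earlier part 2 interim reports contained.

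**What to change.** 1. Restore the ABR for part 2 alone with prophylaxis regimens combined, on actual part 2 person-time with a log-time offset, next to the accumulated ABR.
2. Add ABR by 6-month interval, or by year since first dose as already done for patient-reported outcomes. Assign bleeds and person-time to the regimen in use at the time and include all periods on each regimen, so that intervals spanning a switch are split and time after a return is kept.
3. State beside the by-regimen rates that switching depends on bleeding, so differences between regimens or over time within a regimen are partly selection.
4. Replace the reason in SAP section 3. Differing time on trial at entry limits reading the part 2 ABR as a time trend and is handled by item 2.

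The cost is small: two descriptive tables from the bleed and exposure data already used for the accumulated ABR, plus splitting exposure at regimen changes. No new data or test is needed.
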